**6 CLINICAL INVESTIGATION DESIGN**

**6.1 General**

The study has a randomized, counterbalanced design and consists of two phases (see figure 1). We sample participants according to the sampling plan outlined below, to ensure representativeness of the sample. We will oversample by 20% to account for dropout or incomplete data (the *n*'s below represent the desired cell counts, after dropout).

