**Figure 1. Schematic overview of study design.**

Title: Clinical Investigation Plan		Author: [name]		Company Restricted	
DocID: ICBE-2-28674	Version: 2.0	Date: 2019-02-18	Status: Approved	Page: 21 of 35	
IRBMANAGER PILOT – QI PROJECT					

Group	A	B	C	D	E
n	100	100	50	50	100-150
Phase 1 tests	Digital	Paper-pencil	Digital	Paper-pencil	Digital
Phase 2 tests	Paper-pencil	Digital	Digital	Paper-pencil	

All participants of Group A-D in phase 1 will be invited to participate in two assessments that will take place with a time interval of four-five weeks between the two phases to minimize retest effects. Participants will be randomly assigned with minimization for demographic variables (to make sure that the groups do not differ in terms of gender, age, education level, and ethnicity) to one of the following groups:

- Group A ( $n=100$ ) completes digital tests in phase 1 and paper-pencil tests in phase 2,
- Group B ( $n=100$ ) completes paper-pencil tests in phase 1 and digital tests in phase 2,
- Group C ( $n=50$ ) completes digital tests in both phases,
- Group D ( $n=50$ ) completes paper-pencil tests in both phases,
- Group E ( $n=100-150$ ) only completes digital tests in one phase (50% of group E will be enrolled in phase 1 and the other 50% of group E will be enrolled in phase 2).

The data of group A and B are used to compare score distributions within-subjects

The data from groups A-D (phase 1) are used to compare score distributions between-subjects (aim 1).

The data of group C and D are used to assess and compare test-retest reliability (aim 1) and assess reliable change indices (aim 3).

The data of group A (phase 1), group C (phase 1) and group E are used to estimate regression based norms for the digital tests (aim 3), as well as to estimate factor loadings for the structural equation model (aim 4).

The data of group A (phase 1), group B (phase 1), group C (phase 1) and group D (phase 1) are used to compare construct validity (aim 1).

Participants will be randomized with minimization for demographic variables (gender, age, education level, ethnicity).

The purpose of adding the 100-150 participants in Group E is to increase the sample size of participants who completed the digital tests for the first time for the norm data to 250-300.

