**Aim 1 comparison of psychometrics.**

Hypothesis A: Digital and paper-pencil test scores are comparable.

For each test, we will first compute age-only referenced scores for digital and paper-pencil version separately. Referenced scores are computed based on the regression based norms (procedure described below under aim 3) and are represented as z-scores indicating a participant's deviation from what would be expected based on the norm sample for a participant with identical demographic characteristics. We then compute the correlation between digital and paper-pencil referenced scores within participants in group A and B (which are the groups in which participants completed both digital and paper-pencil versions of the tests), which needs to be  $r > .6$  to be considered comparable. Our planned sample size allows us to detect a correlation of  $r > .2$  with 80% power. We also perform an equivalence test for each test, comparing the distribution of digital normed scores with paper-pencil normed scores, using a two-one-sided-t-test approach (TOST; Schuirmann, 1987), with equivalence bounds of  $\pm .3$  sd, which we have 99% power to detect. Our planned sample size would allow us to detect equivalence with bounds of at least  $\pm .21$  with 80% power.

Hypothesis B: Test-retest reliability is comparable.

Test-retest reliability will be tested by examining for each test the correlation between the digital tests in phase 1 and phase 2 (group C) and comparing this to the correlation between the paper-pencil tests in phase 1 and phase 2 (group D). High test-retest correlations are expected ( $r > 0.7$ ), except for the ROCFT copy condition, since the scores of this condition generally show a moderate ceiling effect. The planned sample size for group C and group D each yield 80% power to detect  $r > .37$ .

Hypothesis C: Construct validity is comparable.

Construct validity will be investigated by means of two confirmatory factor analyses (CFA), one for each group (digital vs. paper-pencil). We expect to see that the factor structure that fits the paper-pencil data (phase 1, group B & D) well, will also fit the digital data (phase 1, group A & C) well. Assuming that at most two variables per test are included in the CFA, the subject-to-variable ratio is near 10:1 for each CFA.

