**Aim 3. Estimate regression-based norms and reliable change indices**

Title: Clinical Investigation Plan		Author: [name]		Company Restricted
DocID: ICBE-2-28674	Version: 2.0	Date: 2019-02-18	Status: Approved	Page: 26 of 35
IRBMANAGER PILOT – QI PROJECT				

The data collected can be used to establish regression-based norms. 250 (up to 300) participants (group A&C, phase 1 and group E) will be included in the norm group. These norms can be used for the IntelliSpace Cognition tool and may be updated at a later point in time.

Reference scores (for age, educational level, gender, and ethnicity) will be generated using linear regression techniques. We will additionally estimate regression based reliable change indices.

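### The between-subjects phase 1 comparison uses age-only scores although allocation is minimized on four factors; if the other three predict scores, it is conservative and loses a modest amount of power

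*Combined protocol and SAP*

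**What the plan says.** - **Allocation** (section 6.1): "Participants will be randomized with minimization for demographic variables (gender, age, education level, ethnicity"). The stated aim is that the groups should not differ on these variables.
- **Comparisons** (section 6.1): two are planned for score distributions. "The data of group A and B are used to compare score distributions within-subjects", and "The data from groups A-D (phase 1) are used to compare score distributions between-subjects (aim 1").
- **Scores for Hypothesis A** (section 7, Aim 1): "we will first compute age-only referenced scores for digital and paper-pencil version separately". The next sentence describes the resulting z-score as the deviation from what would be "expected based on the norm sample for a participant with identical demographic characteristics". Age-only referencing and matching on all demographics are not the same thing, and the two statements need reconciling.
- **Equivalence test** (section 7, Aim 1): a TOST with bounds of ±.3 SD, a stated power of 99%, and a stated bound of ±.21 at 80% power. The text does not say whether the test is paired or between subjects, and it names no covariate-adjusted model.
- **Other use of the same factors** (section 7, Aim 3): "Reference scores (for age, educational level, gender, and ethnicity) will be generated using linear regression techniques". All four variables are therefore collected and treated as predictors of score.

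**The concern.** Minimization makes the digital and paper groups alike on gender, education and ethnicity. If those factors predict scores, the true sampling variation of the mode difference is smaller than under simple randomization. An analysis that leaves them out keeps their variance in the residual, so it does not report that gain: the interval is too wide and the equivalence test is harder to pass than it should be.

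This matters most for the phase 1 A–D comparison. Every score there comes from a first exposure, so retest effects do not enter, but two separate groups of people are compared and precision is lower. The plan gives no power for this comparison. Hypothesis A is applied to each of ten tests, so an avoidable loss of precision recurs across the battery and bears on the claim in section 5 that digital and paper psychometrics are similar.

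**Working it through.** **Inputs from the documents.** Group sizes are A 100, B 100, C 50 and D 50. Section 6.1 says these "represent the desired cell counts, after dropout", so no further dropout deduction is made. Phase 1 gives 100 + 50 = 150 digital and 100 + 50 = 150 paper. The margin is ±.3 SD and alpha is .05, taken as one-sided .05 for each half of the TOST.

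**Assumptions.** The true mode difference is 0 and scores have SD 1 in both modes. R² is the share of age-only score variance explained by gender, education and ethnicity. It is not given, so .02 to .20 is shown.

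**Step 1: the plan's own figures.** Power = 2Φ(margin/SE − 1.645) − 1. The bound at 80% power = SE × (1.645 + 1.282).
- Paired, 200 people in A+B, SD of the difference 1: SE = 1/√200 = .0707. Power = 2Φ(4.243 − 1.645) − 1 = 99.1%. Bound = ±.207. Both stated figures are reproduced.
- Two-sample, 150 against 150: SE = √(2/150) = .1155. Power = 2Φ(2.598 − 1.645) − 1 = 66.0%. Bound = ±.338. Neither stated figure is reproduced.
- Two-sample, 200 against 200: 82.5% and ±.293. Two-sample, 100 against 100: 36.6%. Neither fits.

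Of the readings tried, only the paired one gives both figures. In a paired difference each person's gender, education and ethnicity are the same on both sides, so their main effects cancel.

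**Step 2: effect of omitting the three factors between subjects.** Under minimization the true SD of the estimate is about .1155 × √(1−R²), while the age-only analysis still reports .1155.
- Unadjusted power = 2Φ[(.3 − 1.645 × .1155) / (.1155√(1−R²))] − 1.
- Adjusted power, same margin = 2Φ[.3 / (.1155√(1−R²)) − 1.645] − 1.

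| Assumed R² | Interval too wide by | Unadjusted power | Adjusted power | Gain (points) |
|---|---|---|---|---|
| .02 | 1.0% | 66.4% | 67.3% | about 1 |
| .05 | 2.6% | 67.2% | 69.3% | about 2 |
| .10 | 5.4% | 68.5% | 72.6% | about 4 |
| .20 | 11.8% | 71.4% | 79.2% | about 8 |

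The proper comparator is the unadjusted column, not 66.0%: minimization already lowers the true variance even when the analysis ignores it.

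**Step 3: simulation check.** Minimization was simulated for 300 people over 1,500 runs, with the education and ethnicity mix taken from the totals in the sampling table.
- R² .05: true SD .1135 against mean reported SE .1151; power 66.6% unadjusted, 68.1% adjusted.
- R² .20: .1038 against .1156; power 68.5% unadjusted, 77.9% adjusted. The type I error at the margin was 2.9% instead of 5%.

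Simulation error on a power near 70% is about √(.7 × .3/1500) = 1.2 points. The powers are lower than the formulas give, by up to about 3 points, but the pattern is the same.

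**Step 4: the scale of the margin.** If adjustment is done by switching to fully referenced z-scores, with ±.3 of their own smaller SD, margin and SE both shrink by √(1−R²). Their ratio does not change and power stays at 66.0%. The gain exists only if the margin is held on one scale.

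**The case against.** Three arguments carry weight.

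1. **The plan may intend only a paired TOST.** Section 7 does not assign the TOST to either design, and its power figures fit the paired one. This stands, and it limits the point. But section 6.1 commits to a between-subjects comparison, and the only scores defined for Hypothesis A are the age-only ones.

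2. **Age-only referencing may be deliberate.** Section 3 says the product's domain scores are referenced by age and only optionally by gender, education and ethnicity, so equivalence on that basic score is a sensible target. This also stands, as a reason to keep the age-only SD as the scale. It is no reason to leave allocation factors out of the model that estimates the mode difference.

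3. **The size is unknown and may be trivial.** At R² .02 the gain is about 1 point. This stands.

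A reader might also infer that the stated 99% power is too high, or that the current intervals are invalid and could produce a false equivalence claim. The documents support neither. The 99% belongs to the paired test, where these factors cancel. In the between-subjects test the error runs the safe way: intervals are too wide and the type I error falls below 5%.

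**Conclusion.** The point holds for the between-subjects phase 1 comparison only, and as a conditional loss of efficiency. If gender, education and ethnicity explain 2% to 20% of score variance beyond age, the age-only analysis reports an interval 1.0% to 11.8% too wide and gives up about 1 to 8 points of power at ±.3 SD. These figures assume a true difference of 0, equal SDs, the planned cell sizes and effective balance from minimization.

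It would be tempting to read the gain as 66% to 79%, or to expect adjustment to make this comparison adequately powered. The first uses the wrong starting point, as Step 2 shows. The second fails because adjusted power reaches 80% only if R² is at least about .21, and 99% only at about .62. The larger gap is that no power is stated for this comparison: about 66% before adjustment, with an 80% bound of about ±.34, outside the plan's own margin.

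**What to change.** In section 7, Aim 1, Hypothesis A:

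- For the phase 1 A–D comparison, regress the score on mode, age, gender, education and ethnicity. Declare equivalence if the 90% confidence interval of the mode coefficient lies within ±.3 of one fixed SD.
- Define that SD as the age-adjusted paper SD. The raw SD would widen the margin relative to the current age-referenced scale; the SD of fully referenced scores would shrink it and remove the gain.
- Put both versions on this common scale without centring each on its own norm, since separate centring would remove the difference being tested.
- Keep the age-only analysis as a sensitivity analysis.
- State that the 99% power and ±.21 bound apply to the paired A/B test, and that the between-subjects test has about 66% power at ±.3 before adjustment.
- Reconcile the age-only wording with the description that refers to identical demographic characteristics.

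The cost is a few sentences and no new data. With linear age (1 term), gender (1), education in three levels (2) and ethnicity in four (3), the model uses 7 of the 298 residual degrees of freedom and leaves 291.

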### Primary hypotheses

The following primary hypotheses will be tested in the study:

Aim 1.

- A. Digital and paper-pencil normed test scores are comparable. We consider the two versions of a test comparable when the digital normed score is on average within .3 sd of the paper normed score and the two normed scores correlate at least .6.
- B. Test-retest reliability of the digital tests is comparable to test-retest reliability of the paper-pencil tests. We consider the reliability to be comparable when we observe no significant difference in a z-test between the digital and the paper-pencil test-retest correlations.

Title: Clinical Investigation Plan		Author: [name]		Company Restricted	
DocID: ICBE-2-28674	Version: 2.0	Date: 2019-02-18	Status: Approved	Page: 20 of 35	
IRBMANAGER PILOT – QI PROJECT					

C. Construct validity of the digital tests is comparable to the construct validity of the paper-pencil tests. We consider construct validity to be comparable when confirmatory factor analysis yields the same factor structure for digital and paper-pencil tests.

Aim 2.

D. The score(s) provided by the ROCFT and Clock Drawing Test scoring algorithms on ISC are correlated highly (> .8) to the score provided by manual scoring for the same drawings.

Aims 3 & 4 have no accompanying hypotheses.

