  - The examinee must not be currently taking medication that might impact test performance (e.g., anti-convulsants, antipsychotics, benzodiazepines, psychostimulants, opioids, tricyclic antidepressants, some norepinephrine reuptake inhibitors). Most antihypertensive medications and statins are acceptable.
  - If previously diagnosed with any physical condition or illness that might depress test performance, illness must not interfere with normal cognitive functioning at work, school, ADLs, etc. Diabetes, hypothyroidism, and hypertension are acceptable if controlled.
  - Exclude primarily nonverbal or uncommunicative. Must not have a diagnosis of aphasia.
  - Examinees should not have received neuropsychological testing although previous MMSE testing is allowed if more than 6 months prior
  - Examinee must not be seeking medical diagnostic procedures for cognitive difficulties from a medical professional.
  - Non-valid health insurance in USA.

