## 7 STATISTICAL CONSIDERATIONS

**Statistical design, analyses and power considerations**

Below we describe the planned analyses for each aim and hypothesis. The tests are scored by two raters (with 30% overlap) and inter-rater agreement is assessed prior to proceeding with the following analyses. All correlations mentioned below are Pearson correlations. Retest correlations are corrected for the variability of the normative sample (Allen & Yen, 2002; Magnusson, 1967). Correlation between paper and pencil measures are corrected for measurement error (Padilla & Veprinsky, 2012). In our power analyses we assume an alpha of .05.

Title: Clinical Investigation Plan		Author: [name]		Company Restricted	
DocID: ICBE-2-28674	Version: 2.0	Date: 2019-02-18	Status: Approved	Page: 25 of 35	
IRBMANAGER PILOT – QI PROJECT					

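### Hypothesis A takes one digital-paper correlation over two opposite test orders with no order term, so a practice gain lowers it and can fail a comparable test on the .6 rule

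*Combined protocol and SAP*

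**What the plan says.** Section 5 (Primary hypotheses, Aim 1 A) makes comparability depend on two conditions: the mean digital normed score lies within .3 SD of paper, and "the two normed scores correlate at least .6". Section 7 (Aim 1, Hypothesis A) gives the analysis: "We then compute the correlation between digital and paper-pencil referenced scores within participants in group A and B". The same section says "All correlations mentioned below are Pearson correlations" and names no partial, by-group or by-order form.

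In Section 6.1, group A "completes digital tests in phase 1 and paper-pencil tests in phase 2" and group B "completes paper-pencil tests in phase 1 and digital tests in phase 2". Each has n = 100, and these numbers "represent the desired cell counts, after dropout".

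Scores are referenced on age only before they are correlated. Under Aim 3, the digital norms come from groups A and C in phase 1 and from group E, all first exposures. The source of the paper norms is not stated.

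Practice is addressed only through spacing. Section 6.1 gives a "time interval of four-five weeks between the two phases to minimize retest effects", while the Executive Summary gives two weeks for the same purpose. Those two statements need to be reconciled. No size of practice gain is given anywhere.

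Section 7 also mentions a correction of correlations for measurement error, in wording that does not make clear whether the digital-paper correlation is meant.

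**The concern.** A and B form a two-period crossover. Counterbalancing cancels an equal practice gain from the mean digital-paper difference, but it does not cancel it from a correlation computed over both groups. In A the second-session gain sits in the paper score, in B in the digital score. The two group centres therefore lie on a line of negative slope, and merging them subtracts from the covariance and adds to both variances.

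Age-only norming does not remove this. The same age reference is applied to both groups, and the groups are balanced on age by minimization, so the gap between their centres survives.

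The .6 rule is half of a primary pass/fail criterion and supports the claim that digital tests have psychometrics similar to paper. The penalty depends on each test's own retest gain, so the ten tests would face different effective thresholds. A failure could not be attributed to format rather than to practice.

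**Working it through.** **1. Is the correlation pooled?** The word does not appear, so I checked the plan's power figures (alpha .05).

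Power to detect r = .2, two-sided, Fisher z: Φ(atanh(.2)·√(n−3) − 1.960), with atanh(.2) = .2027.
- n = 200: Φ(2.845 − 1.960) = 81%
- n = 100: Φ(1.997 − 1.960) = 51%

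Paired TOST at zero true difference, bound b in SD of the difference: 2Φ(b√n − 1.645) − 1.
- n = 200: 99.1% at b = .30 and 81.5% at b = .21
- n = 100: 82.5% and 35.1%

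The plan states 80% for r > .2, 99% at .3 and 80% at .21. Only n = 200, that is A and B together, reproduces these.

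**2. Effect of pooling.** Assume unit SD and correlation r within each order, and the same gain d in both. The mean vectors (digital, paper) are (0, d) in A and (d, 0) in B. With equal group sizes, pooling adds d²/4 to each variance and subtracts d²/4 from the covariance:

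pooled r = (r − d²/4) / (1 + d²/4)

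Setting this equal to .6 gives the within-order correlation needed: r = .6 + .4d².
- d = .2: .616
- d = .3: .636
- d = .5: .700

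Examples: r = .65 and d = .3 gives (.65 − .0225)/1.0225 = .614. With d = .5 it is (.65 − .0625)/1.0625 = .553. For r = .70 the values are .663 and .600.

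**3. Chance of passing if .6 is applied to the uncorrected r** (simulation, 100 + 100, 6,000 runs):

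| Within-order r | d = 0 | d = .2 | d = .3 | d = .5 |
|---|---|---|---|---|
| .62 | 67% | 54% | 37% | 6% |
| .65 | 88% | 78% | 62% | 16% |
| .70 | 99% | 98% | 93% | 50% |
| .75 | 100% | 100% | 99.8% | 87% |

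After centring within group, the pass rate is about 88% at r = .65 and 99% at r = .70 for every d in the table.

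**4. If the measurement-error correction applies.** Assume reliability .7 for both versions; Section 7 expects retest correlations above .7 for most tests. Corrected value = pooled r / .7. Pass rates are simulated with reliabilities estimated from 50 + 50.
- True corrected r = .70, so observed within-order r = .70 × .7 = .49. The corrected pooled value is .653 at d = .3 and .575 at d = .5. The pass rate goes from about 87% (d = 0) to 74% and 43%.
- Observed within-order r of .65 or .70. At d = .5 the corrected pooled value is .553/.7 = .79 or .600/.7 = .86. The pass rate stays at about 99% or more.
- The gain that brings the corrected value down to .6 is .31, .44, .63 and .89 for a true corrected r of .65, .70, .80 and 1.0.

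**5. Unequal gains.** The covariance term becomes the product of the two gains divided by 4. With r = .62 and gains of .5 and .2, pooled r = (.62 − .025)/√(1.0625 × 1.01) = .574. The marked fall requires gains of the same sign.

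**The case against.** The strongest reply concerns size. The garbled sentence on measurement error most naturally refers to the digital-paper correlation, because retest correlations receive their own correction in the sentence before it. If so, the table in step 3 of the working is not what the plan would deliver. An observed within-order r of .70 would pass about 99.9% of the time at d = .5 and 78% at d = .8. This stands as a limit. Which reading applies cannot be settled from the text, so both are shown.

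It is also fair that the uncorrected effect is modest below about d = .3. It matters chiefly for tests whose within-order correlation lies between .6 and .6 + .4d². The documents give no d. The eligibility rule under which "previous MMSE testing is allowed if more than 6 months prior" suggests that the sponsor takes prior exposure seriously, but it says nothing about the size of a gain.

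A reader might infer three stronger things that the documents do not support:
- **That pooling could produce a false claim of comparability.** With gains of the same sign it only lowers r.
- **That unequal carry-over biases the mean comparison.** That needs gains that differ by order, and nothing in the documents indicates this. The planned phase 1 comparison between subjects in groups A-D is free of carry-over in any case.
- **That groups C and D could be used to test for carry-over, with a switch to the phase 1 comparison if it appears.** C and D show same-format gains, not the cross-format gains that matter. The switch would also let the data choose the estimator for a pass/fail test. And 150 against 150 gives TOST power of about 66% at .3 SD (2Φ(.3/√(2/150) − 1.645) − 1), against the stated 99%.

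**Conclusion.** The concern holds in a limited form. As written, Hypothesis A specifies a single Pearson correlation over two opposite orders with no order term, and the plan's power figures confirm n = 200. Any same-sign practice gain biases that correlation downward, by an amount that differs between tests.

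How much this matters depends on two things the documents leave open: the gain d, and whether .6 applies to the corrected correlation. Without correction, a gain of .3 to .5 SD cuts the chance of passing from 88% to between 62% and 16% at a within-order r of .65, and from 99% to between 93% and 50% at .70. With correction at an assumed reliability of .7, tests with a modest corrected correlation or a large gain are affected, and most others are not. These figures assume equal variances, equal gains in both orders and 100 completers per group.

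The risk is a test wrongly judged not comparable. This should be fixed before the data are analysed, but it does not undermine the design or the mean-equivalence test.

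**What to change.** In Section 7, Hypothesis A, specify that the digital-paper correlation is computed within each order and then combined before .6 is applied. Any one of these will do: average the Fisher z values of groups A and B, centre scores within group, or use the partial correlation given group. Name the choice in advance, because adopting it after a test has failed would look post hoc.

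In the same place, state whether .6 applies to the corrected or the uncorrected correlation, and reword the measurement-error sentence so that its target is clear.

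The cost is a few words in the plan, a line or two of code and one degree of freedom for the order term. No extra participants or data are needed. No carry-over test or conditional change of estimator is needed for this point.

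### The two correlation power figures under Aim 1 test against zero and do not describe the plan's own decision rules; this matters most for Hypothesis B, where non-significance counts as success

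*Combined protocol and SAP*

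**What the plan says.** Section 5 (Primary hypotheses) sets the rules. Under Hypothesis A, a digital version passes if its scores meet two conditions: "on average within .3 sd of the paper normed score and the two normed scores correlate at least .6". Under Hypothesis B, retest reliability is comparable "when we observe no significant difference in a z-test between the digital and the paper-pencil test-retest correlations".

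Section 7 (Aim 1) gives the power. For Hypothesis A: "Our planned sample size allows us to detect a correlation of" r > .2 with 80% power. For Hypothesis B: "The planned sample size for group C and group D each yield 80% power to detect" r > .37. The same section expects retest correlations above 0.7, except for the ROCFT copy condition. It also gives power for the equivalence test on means (99% at ±.3 sd, 80% at ±.21), which covers the mean part of Hypothesis A but not the correlation part.

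The opening of section 7 states: "In our power analyses we assume an alpha of .05". It does not say whether tests are one- or two-sided. It adds that retest correlations will be corrected for the variability of the normative sample, and that a further set of correlations will be corrected for measurement error. The wording of that second statement is unclear, but the digital-paper correlation is the natural reading. The later headings "Significance and power" and "Pass/fail criteria" only refer back to this text.

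**The concern.** A power statement is useful when it refers to the test that decides the hypothesis. Here the hypotheses turn on a .6 threshold and on a comparison between two groups. The figures quoted appear to answer another question, namely whether a single correlation differs from zero. A reader could take 80% power as assurance about decisions to which it does not apply.

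The consequences differ for the two hypotheses. For A, the plan does not tell the reader how likely a test version is to pass. For B, success is a non-significant result, so a weak test favours the conclusion the sponsor wants. Aim 1 is also the stated support for claim 3 in section 5, that the digital tests have psychometrics similar to those of the paper tests.

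**Working it through.** **Inputs.** Groups A and B have 100 each, so there are 200 within-person pairs. Groups C and D have 50 each. Section 6.1 says these counts are after dropout. Alpha is .05, taken as two-sided. True correlations are assumptions shown over a range; the plan itself gives only r > 0.7 for retest.

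**1. Reproducing the plan's figures as tests against zero.** By Fisher z, power = Φ(atanh(r)·√(n−3) − 1.96).
- n = 200, r = .2: atanh(.2)·√197 = 2.845, so power is Φ(0.885) = 81%. The noncentral-t form gives 82%.
- n = 50, r = .37: atanh(.37)·√47 = 2.663, so power is Φ(0.703) = 76%. The noncentral-t form gives 79%, with 80% reached at r = .375.

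The null value is not written in the plan. Zero is inferred from this agreement and from the plan quoting the second figure for each group separately.

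**2. Hypothesis B on its own rule.** The z-test compares two independent correlations, with SE = √(1/47 + 1/47) = 0.206. For 80% power the difference on the Fisher z scale must be (1.96 + 0.842) × 0.206 = 0.578. The lower correlation is tanh(atanh(higher) − 0.578):

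| Higher correlation | Lower correlation detectable with 80% power |
|---|---|
| .70 | .28 |
| .80 | .48 |
| .90 | .71 |

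For assumed pairs, the chance of declaring comparability is one minus the power:

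| True pair | Power | Declared comparable |
|---|---|---|
| .70 vs .60 | 13% | 87% |
| .70 vs .50 | 34% | 66% |
| .70 vs .40 | 58% | 42% |
| .80 vs .60 | 50% | 50% |

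For .70 vs .50 the step is (0.867 − 0.549)/0.206 = 1.54, and Φ(1.54 − 1.96) = 34%. These figures leave out the correction for normative-sample variability.

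**3. Hypothesis A on its own rule.** The rule is a cut-off on the estimate. With an uncorrected Pearson correlation and n = 200, the pass probability is Φ((atanh(ρ) − atanh(.6))·√197). If the correlation is corrected for measurement error, its sampling error is larger. The second row below comes from a simulation that assumes a reliability of .7 to .9 in each version, each estimated from 50 participants.

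| Correlation analysed | True ρ = .637 | True ρ = .70 |
|---|---|---|
| Uncorrected Pearson | 80% | 99% |
| Corrected, reliability .7 to .9 | about 67% to 76% | about 87% to 97% |

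An observed uncorrected .60 has a one-sided 95% lower limit of tanh(0.693 − 1.645/√197) = .52.

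**The case against.** The plan never says in so many words that r > .2 is the power for the .6 rule, or that r > .37 is the power for the two-group z-test. That is fair, and it means that any misleading effect is an inference. But these are the only correlation power figures given, they stand under the hypotheses they appear to support, and the later headings on power and pass/fail criteria add nothing. The mismatch stands.

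A reader might infer several stronger things that the documents do not support.
- **That .37 is an arithmetic error.** The noncentral-t calculation reaches 80% at .375, and a one-sided test has more than 80% power at .37 (about 85% by Fisher z). The gap depends on the method and changes no decision.
- **That 200 pairs are too few for the .6 rule, because a version truly at .6 has about an even chance of passing.** That holds for an essentially unbiased estimate against any such cut-off at any sample size. At a true .70 the pass probability is high under either form of the correlation.
- **That the reliability comparison can detect only a collapse.** This is too strong. From .90 it detects a fall to .71 with about 80% power, and values that high are within the plan's expectation of r > 0.7.
- **That one number, 80% at a true .64, can simply be put in for Hypothesis A.** It holds only for an uncorrected correlation, and section 7 plans a measurement-error correction.

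**Conclusion.** The point holds as a mismatch between the power statements and the decision rules. It is not a calculation error, and it does not show that the sample is too small for Hypothesis A.

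It has most weight for Hypothesis B. A non-significant z-test with 50 per group is weak evidence of comparable reliability when true retest correlations are near .70: a true digital value of .50 against .70 on paper would pass about two times in three. This rests on assumed true values, a two-sided .05 test and no range correction. Modelling that correction would change the sampling error, but it would not make a test against zero relevant to the comparison.

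For Hypothesis A the gap is one of disclosure. The size of the pass probability depends on whether the correlation is corrected and on reliabilities that the plan does not give.

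**What to change.** Replace both power sentences in section 7, Aim 1.

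- **Hypothesis B.** State the difference that the 50-versus-50 z-test can detect with 80% power (for example .70 vs .28). Say that a non-significant result does not by itself show comparable reliability. Report the confidence interval for the difference between the two retest correlations for each test.
- **Hypothesis A.** State first whether the digital-paper correlation judged against .6 is corrected for measurement error. Then give the probability of passing over a range of true correlations for that version of the statistic, with the assumed reliabilities shown. Report the lower 95% limit of the correlation beside the .6 rule.

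The cost is restated, less favourable figures and two added intervals per test. No new participants and no change to the design are needed.
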